6.5.5 Vital Signs

All vital signs will be recorded on the case report form. Vital signs may be obtained with the subject in the supine or upright position. Care will be taken to obtain subsequent recordings with the subject in the same position (supine or upright). Although allergic or other immediate adverse reactions are not anticipated, subjects will be monitored for at least 60 min post injection. Vital signs will be obtained at 3 time points pre-injection (anticipated to be within 30 mins prior to injection of ^{64}Cu -DOTA-ECL1i although it might be longer if delays in quality control testing result in delay of study drug injection), at the completion of dynamic imaging and at study discharge. Vital signs will include the following: heart rate, systolic blood pressure, diastolic blood pressure, respiratory rate, and body temperature. The following changes from baseline will be considered noteworthy:

Heart rate:	> 30 beats per min
Systolic blood pressure	> 40 mm Hg
Diastolic blood pressure	> 30 mm Hg

Noteworthy changes will be documented on the Principal Investigator Data Safety Review Form. The Principal Investigator will indicate on the form whether or not the changes in vital signs are clinically significant. If clinically significant, the principal investigator will assess the causality of the change to the injection of ^{64}Cu -DOTA-ECL1i.. If a clinically significant change of a vital sign is noted and assessed as being attributable to ^{64}Cu -DOTA-ECL1i injection by the Principal Investigator on the Data Safety and Review CRF, it will be reported on the adverse event log.

6.5.6 Clinical Laboratory Testing

Laboratory tests will consist of the following: standard CBC, and comprehensive metabolic panel obtained at the following time points:

- Baseline: Baseline labs may be obtained anytime within 21 days or immediately prior to ^{64}Cu -DOTA-ECL1i injection and can be done as standard of care or for research purposes.
- Discharge: At least 60 minutes post injection or prior to study discharge.

Approximately 15 mL of blood will be collected for clinical laboratory testing, serum stability / metabolite analysis.

Labs obtained at baseline prior to injection of ^{64}Cu -DOTA-ECL1i will be compared to labs obtained at study discharge. The following changes from baseline clinical laboratory values are considered to be noteworthy and require assessment as to clinical significance when they fall outside of normal limits. Clinically significant changes in laboratory values which are attributed to ^{64}Cu -DOTA-ECL1i injection should be followed up until they return to baseline or normal levels, or until follow-up is no longer warranted. Laboratory values that are abnormal at baseline but move into normal range will not be considered clinically significant. If a clinically significant change of a laboratory value is noted, it will be reported on the PI Data Safety and Review Form so that the PI can assess the change as being attributable to ^{64}Cu -DOTA-ECL1i injection. All clinically significant laboratory changes as identified below

which are identified by the PI as being attributable to ^{64}Cu -DOTA-ECL1i will be recorded on the adverse event log.

Clinically Significant Laboratory Values

Analyte	Change from baseline
Hemoglobin	> 2g/dL
WBCs	> 1 K/mm ³
Neutrophils	> 10 %
Lymphocytes	> 10%
Platelets	> 50 K/mm ³
Creatinine	> 0.75 mg/dL
BUN	> 20 mg/dL
Calcium	> 1mg/dL
Sodium	> 5 mmol/L
Potassium	> 0.5 mmol/L
CO ₂	> 4 mmol/L
ALT (SGPT)	> 150 IU/L
AST (SGOT)	> 100 IU/L
Alkaline Phosphatase	> 150 IU/L
Total Bilirubin	> 0.5 mg/dL
Albumin	> 1g/dL

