6.5.7 Electrocardiograms (ECGs)

A standard 12-lead ECG will be obtained on all subjects at baseline (within approximately 30 mins prior to injection of ^{64}Cu -DOTA-ECL1i although it might be longer if delays in quality control testing result in delay of study drug injection), and at least 60 minutes post injection or prior to study discharge.

The following table lists criteria for normal limits and clinically notable limits for ECGs in adults.

Criteria for Normal Limits and Clinically Notable Limits for ECGs in Adults

	Normal Limits (msec)		Notable Limits (msec)	
ECG Variables	Low	High	Low	High
PR interval	120	200	<120	>200
QRS interval	50	100	< 50	>100
RR interval	600	1000	<600	>1000
QT interval	No lower limit	≥ 460	No lower limit	≥ 460

ECG's which have limits noted to be outside of the table above will be recorded on the PI Data Safety and Review Form where the PI will review and assess as being attributable to ^{64}Cu -DOTA-ECL1i injection. Any ECG recordings identified by the PI as being attributable to ^{64}Cu -DOTA-ECL1i will be recorded on the adverse event log.

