6.10.0 Regulatory and Reporting Requirements

The entities providing oversight of safety and compliance with the protocol require reporting as outlined below. Please refer to Appendix A for definitions and Appendix B for grid of reporting timelines. Adverse events will be tracked from start of treatment through study discharge. All adverse events must be recorded on the toxicity tracking case report form (CRF) with the exception of:

- Baseline adverse events, which shall be recorded on the appropriate study CRF
- Events related to surgery or any testing or procedures performed in preparation for surgery

Reporting requirements for Washington University study team may be found in Section 6.10.1

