APPENDIX A: Definitions for Adverse Event Reporting

A. Adverse Events (AEs)

As defined in 21 CFR 312.32:

Definition: any untoward medical occurrence associated with the use of a drug in humans, whether or not considered drug-related.

Grading: the descriptions and grading scales found in the revised NCI Common Terminology Criteria for Adverse Events (CTCAE) version 5.0 will be utilized for all toxicity reporting. A copy of the CTCAE version 5.0 can be downloaded from the CTEP website.

Attribution (relatedness), Expectedness, and Seriousness: the definitions for the terms listed that should be used are those provided by the Department of Health and Human Services' Office for Human Research Protections (OHRP). A copy of this guidance can be found on OHRP's website: <http://www.hhs.gov/ohrp/policy/advevntguid.html>

B. Suspected Adverse Reaction (SAR)

As defined in 21 CFR 312.32:

Definition: any adverse event for which there is a reasonable possibility that the drug caused the adverse event. "Reasonable possibility" means there is evidence to suggest a causal relationship between the drug and the adverse event. "Suspected adverse reaction" implies a lesser degree of certainty about causality than adverse reaction, which means any adverse event caused by a drug.

C. Life-Threatening Adverse Event / Life Threatening Suspected Adverse Reaction

As defined in 21 CFR 312.32:

Definition: any adverse drug event or suspected adverse reaction is considered "life-threatening" if, in the view of the investigator, its occurrence places the patient at immediate risk of death. It does not include an adverse event or suspected adverse reaction that, had it occurred in a more severe form, might have caused death.

D. Serious Adverse Event (SAE) or Serious Suspected Adverse Reaction

As defined in 21 CFR 312.32:

Definition: an adverse event or suspected adverse reaction is considered "serious" if, in the view of the investigator, it results in any of the following outcomes:

- o Death
- o A life-threatening adverse event

- o Inpatient hospitalization or prolongation of existing hospitalization
- o A persistent or significant incapacity or substantial disruption of the ability to conduct normal life functions
- o A congenital anomaly/birth defect

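### Sections 6.5.5–6.5.7 tie adverse event log entry to the PI's attribution, against the any-cause rule in Appendix A and 6.10.0, and the AE windows in 6.9.0 and 6.10.0 do not fit the follow-up assessment

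*Combined protocol and SAP*

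**What the plan says.** **Entry to the log.** All three safety-measurement sections make the PI's causal judgement the stated condition.

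- Vital signs (6.5.5): "If a clinically significant change of a vital sign is noted and assessed as being attributable to" the tracer injection "by the Principal Investigator on the Data Safety and Review CRF, it will be reported on the adverse event log".
- Laboratory values (6.5.6): clinically significant changes "which are identified by the PI as being attributable to ^{64}Cu -DOTA-ECL1i will be recorded on the adverse event log".
- ECGs (6.5.7): "Any ECG recordings identified by the PI as being attributable to" the tracer go on the log.

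Flagged findings also have a place on a separate PI form. For vital signs, "Noteworthy changes will be documented on the Principal Investigator Data Safety Review Form". Sections 6.5.6 and 6.5.7 likewise send clinically significant laboratory changes and out-of-limit ECGs to a PI review form.

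**Definition and recording rule.** Appendix A defines an AE as "any untoward medical occurrence associated with the use of a drug in humans, whether or not considered drug-related". Section 6.10.0 says: "All adverse events must be recorded on the toxicity tracking case report form (CRF) with the exception of" baseline events and events related to surgery or its preparation. Lack of attribution is not an exception.

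**Forms.** Section 6.12.0 lists eight forms. One, the Adverse Event Log, is named as an AE form, and it is due after follow-up. The PI Data Safety Review is due after follow-up and the AE forms. No toxicity tracking form is listed.

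**Window.** Section 6.9.0 runs safety assessment up to imaging discharge. Section 6.10.0 tracks AEs from start of treatment to study discharge. Section 6.5.8 requires a contact to assess AEs at least 24 hours after administration, normally within 14 days, and the 6.13 calendar marks AE assessment at that contact.

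**The concern.** Under an any-cause definition, attribution is something recorded about an event once it counts as an AE. Sections 6.5.5–6.5.7 use it earlier, to decide whether a finding reaches the AE log at all. In this open-label study the judgement is made by one person, the PI.

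Section 6.5.1 says that data are collected to build the tracer's safety profile. Appendix B puts adverse events into the toxicity table of the semi-annual DSM report and sends the current table to the FDA with the IND annual report. If that table is drawn from a log filtered by attribution, it is not the any-cause summary that its label implies. The mismatched windows raise a second question: whether events first reported at the follow-up contact are within the tracked period.

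**Working it through.** No figure in the plan bears on this point, so the check is a comparison of sections.

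**Step 1: trace one finding through the text.** Suppose that potassium at discharge has moved beyond the 6.5.6 threshold (more than 0.5 mmol/L from baseline) and outside normal limits. The PI judges it untoward and clinically significant, but not due to the tracer.

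| Section | What happens to the finding |
|---|---|
| 6.5.6 | Goes on the PI review form; the condition for log entry is not met |
| Appendix A | Is an AE, because cause does not matter |
| 6.10.0 | Must go on the toxicity tracking CRF; it is neither a baseline nor a surgery-related event |
| 6.12.0 | Lists no toxicity tracking CRF |

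The same trace applies to vital signs under 6.5.5 and to ECGs under 6.5.7.

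**Step 2: one form or two?** If the log and the toxicity tracking CRF are the same form, its entry condition in 6.5.5–6.5.7 contradicts 6.10.0. If they are two forms, the one that holds all AEs has no place in the submission schedule. The text must be reconciled on either reading.

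**Step 3: what feeds the toxicity table?** The routine-AE row of Appendix B and the AE sentence in 6.11.0 carry no attribution limit, and neither names a source form. If the source is the log, the Step 1 finding can be missing from the table. If it is the 6.10.0 CRF, the table may be complete, but that form is unscheduled.

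**Step 4: direction and reach.** Compared with the same log without the condition, the attribution filter can only lower an any-cause count. It acts on three kinds of finding: vital signs, laboratory values and ECGs. The documents put no such condition on symptoms, such as the altered taste in 6.8.0, or on events reported at follow-up. They give no expected number of unattributed findings, so the size cannot be calculated.

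**Step 5: window.** Sections 6.5.5–6.5.7 use study discharge for the last measurements of the imaging day. With that meaning, 6.10.0 closes before the contact required by 6.5.8. Section 6.9.0 says imaging discharge outright, so it conflicts with 6.5.8, 6.12.0 and 6.13 whatever study discharge means.

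**Step 6: order of the forms.** Section 6.5.5 needs the PI's attribution on the review form before log entry, while 6.12.0 has that form follow the AE forms. (The review form's name varies slightly; I take it to be one form.) Taken literally, the condition is assessed after the log is complete. If the PI completes the form in two steps, the difficulty disappears.

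**The case against.** The strongest defence is that the any-cause rule already exists. Section 6.10.0 demands all AEs, 6.10.2 requires events outside expedited reporting to be captured, and 6.13 schedules AE assessment with no causality test. On this view 6.5.5–6.5.7 only triage screening values, many of which are not AEs: the 6.5.7 limits flag an ECG whatever its baseline. Those sections do not expressly bar unattributed findings from the log. This stands in part. The issue is confined to findings that are untoward occurrences and not attributed. But for these the sections give one route to the log, through attribution, and 6.10.0 relies on a form name that the schedule does not contain.

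Several stronger readings are tempting, and the documents do not support them.

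- **That safety data are lost.** Flagged findings remain on the PI review form, which 6.12.0 schedules.
- **That no reporting text limits by cause.** The FDA expedited rows of Appendix B, and 6.10.1.3, concern suspected adverse reactions, which Appendix A defines by a reasonable possibility of causation. Only the routine-AE text lacks a limit.
- **That 6.10.0 certainly excludes follow-up.** Study discharge is undefined there; the imaging-day meaning is inferred from its use in 6.5.5–6.5.7.
- **That the form order is a firm contradiction.** Nothing forbids two-step completion.
- **That a bias in an AE rate can be stated.** Section 6.7.0 plans no any-cause AE rate and no formal statistical review of safety data.
- **That a set number of hours separates early surgery from the follow-up contact.** Section 6.5.8 counts the surgery time from administration and imaging together, and nothing in this point depends on it.

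It is also fair to say that calling the log the only AE form rests on form titles. The content of the PET Imaging Follow up Form is not given.

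**Conclusion.** The point holds as a conflict in the text and should be fixed. The log-entry condition in 6.5.5–6.5.7 does not fit the Appendix A definition or the all-AE rule in 6.10.0, and 6.12.0 does not schedule the CRF that 6.10.0 names. The safety window in 6.9.0 does not fit the follow-up AE assessment; the one in 6.10.0 does not fit it if study discharge means the imaging day.

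Confidence is high on these mismatches and lower on their consequence. Whether the toxetable is incomplete depends on the log being its source, which the plan does not say, and on how many unattributed findings are AEs, which is unknown. The effect is limited to descriptive safety reporting. Safety is not among the 6.2.0 objectives, and no planned analysis changes. The form-order point is minor.

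**What to change.** - **6.5.5–6.5.7:** enter on the log every finding that meets the Appendix A definition of an AE, and record the PI's attribution as a separate field rather than as the condition for entry.
- **6.10.0 and 6.12.0:** use one AE form name, so that the baseline and surgery exceptions clearly apply to it. Name that form, in Appendix B or 6.11.0, as the source of the DSM toxicity table.
- **6.9.0 and 6.10.0:** reconcile with 6.5.8, 6.12.0 and 6.13 so that AE tracking runs through the follow-up contact, and define study discharge.
- **6.12.0 (minor):** state that the PI's attribution is made before the log is closed.

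The cost is wording, a few more log entries, and an attribution field if the log does not already have one (the form is not in the documents). No visit or test is added.

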6.5.7 Electrocardiograms (ECGs)

A standard 12-lead ECG will be obtained on all subjects at baseline (within approximately 30 mins prior to injection of ^{64}Cu -DOTA-ECL1i although it might be longer if delays in quality control testing result in delay of study drug injection), and at least 60 minutes post injection or prior to study discharge.

The following table lists criteria for normal limits and clinically notable limits for ECGs in adults.

Criteria for Normal Limits and Clinically Notable Limits for ECGs in Adults

	Normal Limits (msec)		Notable Limits (msec)	
ECG Variables	Low	High	Low	High
PR interval	120	200	<120	>200
QRS interval	50	100	< 50	>100
RR interval	600	1000	<600	>1000
QT interval	No lower limit	≥ 460	No lower limit	≥ 460

ECG's which have limits noted to be outside of the table above will be recorded on the PI Data Safety and Review Form where the PI will review and assess as being attributable to ^{64}Cu -DOTA-ECL1i injection. Any ECG recordings identified by the PI as being attributable to ^{64}Cu -DOTA-ECL1i will be recorded on the adverse event log.

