6.5.0 METHODS

6.5.1 Study Design

A single center, open-label, baseline-controlled diagnostic imaging study designed to assess the diagnostic quality and CCR2 expression detectability of ^{64}Cu -DOTA-ECL1i imaging with PET/CT. In addition, data will be collected to build the ongoing safety profile of ^{64}Cu -DOTA-ECL1i and uptake will be correlated to in vitro assays of chemokines receptor from clinically obtained biopsy/surgical specimen.

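### ECG review is triggered only by fixed limits on uncorrected QT and ignores the paired baseline, so a large QT rise could pass unprompted; the QT row also needs reconciling

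*Combined protocol and SAP*

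**What the plan says.** Section 6.5.7 provides for paired tracings: "A standard 12-lead ECG will be obtained on all subjects at baseline", "and at least 60 minutes post injection or prior to study discharge". The rule for bringing a tracing to the investigator is: "ECG's which have limits noted to be outside of the table above will be recorded on the PI Data Safety and Review Form". The table sets absolute limits in milliseconds for PR, QRS, RR and QT. Three rows matter here:

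- PR: "PR interval 120 200 <120 >200"
- RR: "RR interval 600 1000 <600 >1000"
- QT: "QT interval No lower limit ≥ 460 No lower limit ≥ 460"

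The columns are normal low, normal high, notable low and notable high. No rate-corrected QT, correction formula or change-from-baseline criterion for ECGs appears anywhere in the document.

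Section 6.5.5 handles vital signs differently: "The following changes from baseline will be considered noteworthy", followed by a list that includes a heart-rate change of more than 30 bpm. Section 6.5.1 calls the trial a "baseline-controlled diagnostic imaging study", and Section 6.7.0 repeats the label. Section 6.5.3.1 gives extension of the tracer's safety profile as the reason for the ECGs. Section 6.7.0 says that the safety data will have no formal statistical review.

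**The concern.** A fixed-limit rule does not address the question that a before-and-after design can answer, namely whether the interval changed after injection. It can err in two directions. A patient can have a large rise and stay inside the limits, so that nothing prompts a review. A patient already outside a limit before injection meets the rule with no change at all.

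Raw QT adds a second difficulty. QT normally shortens as the heart speeds up, so one raw value means different things at the two ends of the RR range that the table calls normal.

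Little else in the plan would prompt a second look at an asymptomatic change. There is no planned statistical review of safety data, Section 6.9.0 keeps the ECGs out of the electronic medical record, and the follow-up in Section 6.5.8 is a verbal assessment. What is at stake is the ECG part of the safety profile, not the imaging results.

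Separately, the QT row as printed makes a value of 460 ms or more both normal and notable, and gives a value below 460 ms no class. The PR, QRS and RR rows do not have this fault.

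**Working it through.** The plan states no figure on this point that could be reproduced. The check is to apply its flagging rules to example pairs of tracings.

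**Inputs from the document.** Section 6.5.7: raw QT is notable at 460 ms or more; RR is notable below 600 or above 1000 ms. Section 6.5.5: heart-rate change is noteworthy above 30 bpm.

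**Assumptions.** The document gives no correction formula, so two common ones are shown as a range, with RR in seconds: Fridericia QTcF = QT / RR^(1/3) and Bazett QTcB = QT / RR^(1/2). Heart rate is taken as 60,000 / RR (ms). PR and QRS are assumed to stay within their limits. The example pairs are illustrative, not observed.

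**Case A: constant rate, QT 360 to 455 ms at RR 800 ms.**
- Heart rate: 60,000/800 = 75 bpm both times, change 0. No vital-sign flag.
- RR is within 600-1000 ms and QT is below 460 ms. No ECG flag.
- Raw rise: 455 - 360 = 95 ms. No formula is needed to see this.
- QTcF: 360/0.8^(1/3) = 388; 455/0.8^(1/3) = 490; rise about 102 ms.
- QTcB: 360/0.8^(1/2) = 402; 455/0.8^(1/2) = 509; rise about 106 ms.

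**Case B: faster rate, QT 400 to 440 ms with RR 1000 to 700 ms.**
- Heart rate: 60 to 60,000/700 = 86 bpm, change about 26 bpm, below the 30 bpm rule. No vital-sign flag.
- RR is within 600-1000 ms and QT is below 460 ms. No ECG flag.
- Raw rise: 40 ms.
- QTcF: 400 to 440/0.7^(1/3) = 496; rise about 96 ms.
- QTcB: 400 to 440/0.7^(1/2) = 526; rise about 126 ms.

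**Outer bound.** The highest whole-millisecond QT below the notable limit is 459 ms. Across the RR range that raises no flag it corresponds to:

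| RR (ms) | QTcF (ms) | QTcB (ms) |
|---|---|---|
| 1000 | 459 | 459 |
| 900 | 475 | 484 |
| 800 | 494 | 513 |
| 700 | 517 | 549 |
| 600 | 544 | 593 |

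The last row pairs the highest unflagged QT with the fastest unflagged rate. It is an extreme, not an expectation.

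**Where the gap ends.** RR below 600 ms or above 1000 ms, raw QT of 460 ms or more, PR or QRS outside limits, or a heart-rate change above 30 bpm each puts the patient on the investigator's form. The entry would then be for that variable, not for a change in corrected QT.

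**The case against.** Several stronger readings are tempting, and the document does not support them.

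- *A QT rise at a faster heart rate is never flagged.* Not so: the flags just listed catch many such patients. The gap is bounded.
- *Only flagged ECGs can reach the adverse event log.* Section 6.10.0 requires all adverse events to be recorded, apart from baseline and surgery-related ones. Section 6.11.0 has the investigator review all patient data at least every six months. The last sentence of Section 6.5.7 is not expressly limited to flagged tracings. These routes exist, but each depends on someone noticing the change; the ECG rule does not prompt it.
- *Laboratory values are flagged by change alone, so the ECG is the sole exception.* Section 6.5.6 compares with baseline, but asks for assessment when the changed value is also outside normal limits. Vital signs are the only pure change rule, so the inconsistency rests on that comparison and on the design label.
- *The rule misses a real drug effect.* The document reports no QT signal, and Section 6.1.0 describes the tracer as safe in ongoing trials. The supportable word is *could*.

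It is also fair to say that flagging a pre-existing abnormality does little harm, because the investigator then judges attribution. If the notable column governs, the QT row's duplication does not alter which tracings are flagged. Safety is not among the objectives in Section 6.2.0, and no imaging or correlation result depends on this rule.

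All of this limits the point. None of it supplies a use for the baseline ECG, or a prompt in Case A.

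**Conclusion.** The point holds in a bounded form. As written, Section 6.5.7 does not prompt review of a post-injection QT rise while raw QT stays below 460 ms, RR stays within 600-1000 ms, heart rate changes by no more than 30 bpm, and PR and QRS stay within limits. Inside that region a raw rise of 95 ms, or a corrected rise of about 96 to 126 ms, can pass.

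The raw figure in Case A rests on the plan's limits alone. The corrected figures rest on the assumed formulas. The document gives no basis for estimating how often such a rise would occur, and none is claimed here.

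The duplicate QT entry is a table inconsistency that needs reconciling. It could be a fault of text conversion and should first be checked against the source PDF.

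The change is worth making because the ECGs are taken to build the safety profile and the paired data are already being collected. It does not affect the primary imaging aims.

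**What to change.** In Section 6.5.7:

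1. State whether QT is rate-corrected and by which formula, and derive the corrected value from the QT and RR already in the table.
2. List each patient's post-minus-pre change in PR, QRS, RR and corrected QT on the investigator's safety review form, beside the absolute values.
3. Reconcile the normal and notable upper entries of the QT row.

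Whether any change or corrected value should count as notable, and at what level, is for the sponsor's clinicians; no limit is proposed here.

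The cost is one extra line per patient for 20 patients, plus one table correction. No new ECG is needed. Patients already imaged can be added wherever both tracings' intervals were recorded. Because the listing covers every patient, the investigator would see all 20 pairs, which is a small burden at this sample size.
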